#### 4.1.3. Baseline participant characteristics (demographic, clinical, and psycho-social)

i) Motivation to quit

- At baseline participants are asked “How motivated are you to stay off cigarettes after you leave this facility?” (response options: not very motivated; moderately motivated; very motivated; extremely motivated)
- At 3-month follow-up, participants who report abstinence from smoking are asked “How motivated are you to remain quit from smoking?” (response options: not very motivated, moderately motivated, very motivated, extremely motivated).

ii) Confidence in ability to quit this time (self-efficacy)

- At baseline all participants are asked: “If you decide to stay off the smokes completely when you leave, how confident are you that you would succeed?” (response options: not at all confident; slightly confident; moderately confident; very confident; extremely confident)
- At 3-month and 9-month follow-ups, *participants who are current smokers* are asked “If you decided to quit smoking permanently in the next 6 months, how confident are you that you would succeed?” (response options: not at all confident; slightly confident; moderately confident; very confident; extremely confident)
- At 3-month and 9-month follow-ups, *participants who report abstinence* are asked “How confident are you that you will succeed in staying quit in the long term?” (response options: not at all confident; slightly confident; moderately confident; very confident; extremely confident)

### iii) Difficulty in quitting

- At baseline all participants asked “How hard do you think it would be for you to stay quit smoking permanently (after you leave this facility)?” (response options: impossible; very hard; hard; easy; very easy).
- At 3-month follow-up, *participants who are current smokers* are asked “How hard do you think it would be for you to quit smoking permanently?” (response options: impossible; very hard; hard; easy; very easy).
- At 3-month follow-up, *participants who report abstinence* are asked “How hard do you think it would be for you to stay quit smoking permanently?” (response options: impossible; very hard; hard; easy; very easy).

### iv) Nicotine dependence

- Two-item Heaviness of Smoking Index consisting of: number of cigarettes per day and timing to first cigarette.
- Scoring: low heaviness of nicotine dependence= 0-2, moderate 3-4, and heavy 5-6.

### v) Alcohol use

- Participants who reported alcohol use (baseline: in 30 days before admission; 3-month follow-up: in time since discharge; 9-month follow-up: current use) were presented a single item from the AUDIT: “How many standard drinks containing alcohol do you have on a typical day when you are drinking?” (response options: 1-2; 3-4; 5-6; 7-9; 10 or more).

#### 4.1.4. Adverse events

Any adverse events reported during the study and follow up period. The number of adverse events will be tabulated by intervention arm. Incidence ratios to be calculated.

#### 4.1.5. Analysis populations

The primary analysis population will be the intention to treat (ITT) population, defined as all participants that were randomised to an intervention arm. Participants

that drop out of the study will have their outcomes imputed using the methods described in the “missing data section”.

Secondary analysis population will include the 1) completers, defined as all participants that were randomised to receive an intervention, and returned for a follow-up survey with complete data (i.e., complete case analysis); 2) the intention to treat population, Participants that drop out of the study will have their outcomes imputed using the methods described in the “missing data section”. 3) the per protocol analysis excluded participants with major protocol violations (e.g. death, pregnancy, study withdrawal, loss to follow-up, non-adherence, non-compliance). Self-reported adherence was defined as having been sent all 12 weeks’ study medication from the study team AND a quitline referral. Self-reported medication compliance was defined as current or previous use of NRT (use of patches for  $\geq 7$  weeks AND any oral form use) or VNP (use for  $\geq 7$  weeks) according to group assignment.

## **4.2. Analysis Methods**

### **4.2.1. Descriptive statistics**

Descriptive statistics will be used to summarize the baseline demographic and clinical characteristics overall and for intervention and control groups. Counts and percentages for categorical data, and means, standard deviations (or medians, interquartile ranges) for continuous data.

### **4.2.2. General Statistical methodology**

Statistical inference for assessing differences between groups for all outcome measures will be within a Bayesian framework. This involves for each outcome specifying a likelihood function, and a prior distribution. Together these form the posterior distribution for the parameters of interest.

### **4.2.3. Samples from the posterior distribution**

Posterior summaries: samples from the posterior distribution will be obtained using the No U-Turn Sampler (NUTS) with 4 Markov chains, as implemented in the brms R package.

### **4.2.4. Assessment of convergence**

Visual inspection of chains, histograms of posterior distributions for all model parameters, Effective sample size,  $R_{hat} \leq 1.1$  indicating chains have converged. If chains have not converged then we will initially attempt to increase the number of iterations, and then try stronger prior distributions.

### **4.2.5. Assessment of fit**

Posterior predictive checks will be used to compare the observed data with the data predicted from the models to look for any discrepancies that might indicate poor model fit. If models indicate poor fit, stronger prior distributions or alternate model distributions will be explored.

#### 4.2.6. Summaries of the posterior distribution

**Posterior mean:** The mean of the converged posterior distribution for the parameter reflecting the between group differences (either absolute or relative) will be presented as the point estimate to 2 decimal places

**Intervals:** 95% credible intervals will be calculated using the highest posterior density (HPD) method and presented to 2 decimal places.

**Probability of direction:** The one-sided probability that the difference between treatment and control is greater than zero will be presented (representing a beneficial treatment effect). This is calculated as the proportion of posterior samples that are of sign that is favorable to the intervention (either +’ve or -’ve)

**Bayes Factors:** The relative evidence of a treatment effect compared to no treatment effect will be calculated. The marginal likelihood of models with and without the treatment effect will be calculated using a bridge sampler as implemented in the brms R package. The ratio of these likelihoods is the Bayes factor. A Bayes factor greater than 1 indicates there is more evidence the treatment is effective compared to no treatment effect. Bayes factor categories can be interpreted as substantial (3.2 to 10), strong (10 to 32), very strong (32 to 100), decisive (>100).

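### The Bayes factor measures evidence of a difference in either direction, but SAP 4.2.6 reads any value above 1 as evidence that the treatment is effective

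*SAP*

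**What the plan says.** SAP section 4.2.6 lists four summaries for each modelled comparison:

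- **Point estimate.** The posterior mean "for the parameter reflecting the between group differences (either absolute or relative) will be presented as the point estimate".
- **Interval.** "95% credible intervals will be calculated using the highest posterior density (HPD) method".
- **Probability of direction.** A one-sided probability of benefit: "This is calculated as the proportion of posterior samples that are of sign that is favorable to the intervention".
- **Bayes factor.** "The marginal likelihood of models with and without the treatment effect will be calculated using a bridge sampler", and the ratio of the two is reported.

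The Bayes factor paragraph opens neutrally, as relative evidence for an effect against no effect. It then gives the reading "A Bayes factor greater than 1 indicates there is more evidence the treatment is effective compared to no treatment effect" and adds grades that "can be interpreted as substantial (3.2 to 10), strong (10 to 32), very strong (32 to 100), decisive (>100".

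Sections 4.3.1 and 4.3.2 give the treatment parameter a non-informative prior, with no distribution, scale or sign restriction. The null hypothesis in section 3.5 is equality of the two proportions.

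**The concern.** An effect and effectiveness are different things. A model that contains a treatment term of either sign gains support over the model without it when the arms differ enough, whichever arm does better. The Bayes factor paragraph starts from the undirected quantity and ends with a directed conclusion that the calculation cannot supply. The grades attach to the same undirected number.

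The rule reaches every outcome with a model in section 4.3, including abstinence, cravings, relapse and withdrawal. If VNP did clearly worse than NRT on one of these, the pre-specified wording would describe the result as strong or decisive evidence that the treatment is effective. The probability of direction beside it would say the opposite. A pre-specified reading should not contradict the neighbouring summary of the same posterior.

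**Working it through.** **Inputs from SAP section 3.4.** 3% abstinent on NRT and 9% on VNP, two-sided 5%, 80% power, 278 per group, 40% attrition, 926 in total.

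**The plan's own figure.** The usual two-proportion formula gives

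n = [1.96·√(2 × 0.06 × 0.94) + 0.8416·√(0.03 × 0.97 + 0.09 × 0.91)]² / 0.06² = 244.8, so 245.

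With the continuity correction, (244.8/4)·[1 + √(1 + 4/(244.8 × 0.06))]² = 277.1, so 278 as stated. Then 556/0.6 = 926.7, against 926 stated. The sample size is reproduced and does not depend on this point.

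**Counts.** 926/2 = 463 per arm. 463 × 0.03 = 13.9 and 463 × 0.09 = 41.7, so 14 and 42 abstinent.

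**Model.** Two binomials on the logit scale, with log odds a − d/2 (NRT) and a + d/2 (VNP). The site intercept is omitted.

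BF = ∫∫ L(a, d) p(a) p(d) da dd ÷ ∫ L(a, 0) p(a) da

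**Assumed priors** (the SAP gives no scale): d ~ N(0, s) and a ~ N(−3, 1.5), where the second figure is the SD. If p(d) is symmetric about zero and the arms are of equal size, swapping the arms only replaces d by −d, and the ratio is unchanged.

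| Prior SD s | BF, VNP 42 vs NRT 14 | BF, VNP 14 vs NRT 42 | SAP grade for both |
|---|---|---|---|
| 0.5 | 174 | 174 | decisive |
| 1 | 388 | 388 | decisive |
| 2.5 | 274 | 274 | decisive |
| 10 | 77 | 77 | very strong |

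With the wider intercept prior a ~ N(−3, 2.5), the values for s = 1, 2.5 and 10 are 386, 272 and 76. At 278 per arm (8 vs 25 abstinent) under that wider prior they are 26.5, 19.4 and 5.5, again the same in both directions.

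**The other summaries when VNP has the 14.** With s = 2.5 the posterior mean log odds ratio is −1.17 and the equal-tailed 95% interval is −1.81 to −0.57 (the plan asks for HPD). The probability of benefit is below 0.001 for every s in the table.

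**A directed Bayes factor for the same data.** Under a symmetric proper prior, half the prior mass is favourable, so

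BF(benefit vs none) = BF × P(favourable | data) / 0.5 = 2 × BF × probability of direction.

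With the probability of direction below 0.001, this is below 2 × 388 × 0.001 = 0.78 at most. Integrated directly, it is about 0.1 or lower for each s. So data that the sentence would call decisive for effectiveness are evidence against benefit.

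**Size of difference needed.** A small difference does not push the ratio above 1: 20 vs 14 abstinent gives 0.83, 0.55 and 0.24 for s = 0.5, 1 and 2.5.

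**The case against.** The strongest reply is that nobody would be misled. Section 4.2.6 reports the Bayes factor beside a signed mean, an interval and a probability of direction that is oriented outcome by outcome towards benefit. In the example these show inferiority plainly, and no reported number changes if the sentence is reworded. This stands, and it limits the finding to one sentence. It does not rescue that sentence, which states its own conclusion and is not made conditional on any of the other three.

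Four stronger readings are tempting, and the document does not support them.

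- **The plan as a whole treats harm as benefit.** It does not, for the reason just given.
- **The Bayes factor is the trial's success criterion.** No section says so, and the grades are offered as an interpretation. Section 4.4 makes further missing-data analyses depend on evidence of a treatment effect, but names no measure of that evidence.
- **An excess of adverse events would be graded as effectiveness.** A reader might infer this from section 4.2.2: "Statistical inference for assessing differences between groups for all outcome measures will be within a Bayesian framework". But section 4.1.4 plans only this: "The number of adverse events will be tabulated by intervention arm. Incidence ratios to be calculated". Section 4.3 gives adverse events no model, so there is no pair of models to compare.
- **The ratio exceeds 1 whenever the arms differ.** The 20 vs 14 example shows otherwise. The difference must be large enough, the more so under a diffuse prior.

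**Conclusion.** The sentence is wrong as written. It equates evidence for a difference with evidence of effectiveness, and a sufficiently large difference against VNP on a modelled outcome would meet its wording. At the plan's design effect reversed, with 463 per arm, the Bayes factor is about 77 to 388 over the prior SDs tried, while the probability of benefit is below 0.001.

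The figures rest on an assumed normal prior, no site effect, equal arms and symmetric coding of the treatment term. The exact equality of the two directions needs that symmetry. The conclusion needs only that the prior does not restrict the sign. How far the size of the Bayes factor depends on the unstated prior scale is a separate matter.

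**What to change.** Replace the sentence in section 4.2.6 with:

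> A Bayes factor greater than 1 indicates more evidence for a difference between groups, in either direction, than for no difference. It is described as evidence of benefit only when the posterior mean is in the favourable direction, and as evidence of inferiority when it is in the unfavourable direction. It is reported with the probability of direction.

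This costs one sentence. It needs no new data, no change of design and no further model fitting.

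Optionally, also report the benefit-directed Bayes factor, 2 × Bayes factor × probability of direction. This holds for a single treatment parameter under a proper prior symmetric about zero, so the SAP would first have to state that prior and its scale. Once it is stated, the quantity follows from two summaries already planned.

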### 4.3. Statistical models

#### 4.3.1. Primary outcome model

The primary outcome of interest will be assessed in the ITT population using a generalized linear mixed model (GLMM) with logit link function including a random intercept for site and treatment group as a fixed effect. Priors on the treatment parameter (difference in log odds between treatment arms) will be non informative and a power prior (normal distribution) based on previously published data will be used in the sensitive analysis. The random intercept will be modelled on the log-odds scale and assumed distributed as a normal distribution with mean 0 and variance assumed to be distributed from as a half Student-T of 3 degrees of freedom.

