#### 4.3.2. Secondary outcome models

Secondary abstinence outcomes will be assessed in the ITT population, other secondary outcomes in the completers and the ITT population. GLMM will be used to assess the difference in outcomes at follow up between treatment groups or changes from baseline.

All single endpoint outcomes will include a normally distributed random intercept for site (on the scale of the canonical link function for the specific distribution family) and treatment group as a fixed effect with a non informative prior for the treatment effect. The random intercept will be modelled from a normal distribution with mean 0 and a hierarchical variance parameter that is distributed as a half Student-T of 3 degrees of freedom.

For outcomes with multiple time points, the models will additionally include participant id as a random intercept, and parameters for time with an interaction between time and treatment group as fixed effects, all on the scale of the canonical link function for the specific distribution family. Non-informative priors will be used for fixed effects. Participant id

random intercept will be modelled from a multivariate normal distribution with mean 0 and covariance matrix with a non-informative prior (LKJ-Correlation and half Cauchy priors implemented in the brms R package).

A GLMM with a binomial distribution and logit link function will be used to model abstinence outcomes (biochemically verified 7-month continuous abstinence, self-reported 30 day and 7 day point prevalence, abstinence at 3 and 9 months).

Number of cigarettes smoked per day will be compared at each time point using a GLMM with a negative-binomial distribution and log link function. Percentage reduction of at least 50% in the number of cigarettes smoked per day will be assessed with GLMM with a binomial distribution and logit link function.

Craving scores and relapse episodes will be compared using a GLMM with multinomial distribution and a cumulative logit link function, or binomial distribution and logit link depending on the distribution of responses.

Withdrawal scores will be compared using a GLMM with normal distribution and identity link function.

Abstinence from all nicotine/ tobacco products will be modelled using GLMM with a binomial distribution and logit link function.

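### Bayes factors are graded under a treatment prior that is non-informative and has no stated scale, so the grade depends on prior width; and a value above 1 is wrongly read as benefit

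*SAP*

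**What the plan says.** For the primary outcome, SAP section 4.3.1 states that "Priors on the treatment parameter (difference in log odds between treatment arms) will be non informative". Section 4.3.2 does the same for single-endpoint secondary outcomes: "treatment group as a fixed effect with a non informative prior for the treatment effect". Neither gives a distribution, a centre or a scale. A power prior is reserved for sensitivity analysis (4.3.1 and 4.4).

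Section 4.2.6 lists four posterior summaries: the posterior mean, a 95% highest posterior density (HPD) interval, the probability of direction and the Bayes factor. On the last it says: "The marginal likelihood of models with and without the treatment effect will be calculated using a bridge sampler", and "The ratio of these likelihoods is the Bayes factor". It then states: "A Bayes factor greater than 1 indicates there is more evidence the treatment is effective compared to no treatment effect". Fixed bands follow, with cut-points at 3.2, 10, 32 and 100, running from substantial to decisive.

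If chains do not converge, section 4.2.4 would first run more iterations "and then try stronger prior distributions". For poor fit, section 4.2.5 says that "stronger prior distributions or alternate model distributions will be explored". Neither names the parameters concerned.

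Sections 4.4 and 4.5 run the missing-not-at-random analyses only if there is evidence of a treatment effect. They do not say which summary decides this.

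**The concern.** A marginal likelihood is the likelihood averaged over the prior. When the two models differ only in the treatment effect, the prior on that effect is part of the answer, and a wide prior is not neutral. It spreads weight over values that the data rule out, which penalises the model with the effect. A prior chosen to say little for estimation therefore says a great deal in a Bayes factor. With the scale left open, the evidence label reported for each outcome is set largely by a choice that the SAP has not made.

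The stated interpretation is a second, separate error. The comparison is between no effect and an effect of either sign, so a large value supports a difference, not benefit.

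At stake is one reported summary, the only one of the four that carries verbal grades. If it were used for the undefined trigger in 4.4 and 4.5, it could also decide whether the missing-not-at-random analyses are run.

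**Working it through.** **The plan's own figures.** The SAP states no Bayes factor and no prior scale, so there is none to reproduce. The sample size in section 3.4 does reproduce: 3% v 9%, two-sided 5%, 80% power and a continuity correction give 278 per arm, and 556/0.6 = 926.7 against the stated 926.

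**Illustrative data.** 3% and 9% of 278 are 8.3 and 25.0, so take 8 and 25 abstainers. The main analysis counts missing as not abstinent (4.5), so the denominator is 926/2 = 463 per arm. The log odds ratio is ln(25/438) − ln(8/455) = 1.178, with SE √(1/25 + 1/438 + 1/8 + 1/455) = 0.412.

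**Model.** Control logit = α and intervention logit = α + δ, with binomial likelihood L(α, δ). Assumptions not in the SAP: α has a Student-t(3, 0, 2.5) prior, the site effect is omitted, and δ ~ Normal(0, s²) is compared with δ = 0.

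BF10 = ∬ L(α, δ) p(α) N(δ; 0, s²) dα dδ ÷ ∫ L(α, 0) p(α) dα

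By numerical integration:

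| Prior SD s | BF10 | Reading on the SAP scale | Posterior mean of δ | Probability of direction |
|---|---|---|---|---|
| 1 | 17.9 | strong | 0.99 | 0.998 |
| 2.5 | 12.2 | strong | 1.13 | 0.999 |
| 10 | 3.4 | substantial | 1.16 | 0.999 |
| 100 | 0.34 | favours no effect, 1/0.34 = 2.9 to 1 | 1.16 | 0.999 |
| 1000 | 0.034 | favours no effect, 1/0.034 = 29 to 1 | 1.16 | 0.999 |

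**Why it falls as 1/SD.** Once s is large relative to the spread of the likelihood, N(δ; 0, s²) is close to 1/(s√(2π)) wherever the likelihood matters, so BF10 ≈ K/s. Here K = 0.344 × 100 = 34.4, and K/10 = 3.44 against 3.41 computed. The Bayes factor crosses 1 near SD 34. Under an improper flat prior the factor 1/(s√(2π)) is replaced by an arbitrary constant, which carries straight into the ratio, so the Bayes factor is undefined.

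**Cross-check by normal approximation.** N(1.178; 0, 0.412² + s²) ÷ N(1.178; 0, 0.412²) gives 12.5, 8.7, 2.4, 0.25 and 0.025 at the same SDs. The pattern is the same, about 30% lower; the binomial figures are the ones to use.

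**A stronger result.** For 14/463 v 42/463 (3% and 9% of 463), BF10 is 288 at SD 1, 54.9 at SD 10, 5.5 at SD 100 and 0.55 at SD 1000.

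**Direction.** Reverse those arms, with 42/463 abstinent on control and 14/463 on intervention. BF10 at SD 1 is about 453, and the probability of direction for benefit is about 0.0001. Section 4.2.6, read literally, would call this decisive evidence that the treatment is effective. (It is not 288 because the assumed intercept prior is centred at zero and so treats the two arms unequally.)

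**The case against.** The best defence is that the Bayes factor is one of four summaries and is nowhere named as the decision rule. That stands. From SD 2.5 to SD 1000 the posterior mean moves only from 1.13 to 1.16, and the probability of direction does not move at the third decimal. A reader might infer that the primary result is unsafe; the SAP does not support that.

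A reader might also infer that a wide prior makes the Bayes factor favour no effect whatever the data show. That is true only in the limit of infinite width: 14/463 v 42/463 still gives 5.5, or substantial, at SD 100.

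A third tempting reading is that sections 4.2.4 and 4.2.5 authorise strengthening the treatment prior once the fit has been seen. They do not say so. They name no parameter, 4.2.4 tries more iterations first, and 4.3.1 fixes the treatment prior and places the informative one in sensitivity analysis. Variance parameters may well be what is meant. What stands is that the treatment prior is not excluded, and that moving it from SD 100 to SD 1 would multiply the Bayes factor by 17.9/0.344 = 52.

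On direction, the estimate and probability of direction are reported alongside, so a careful reader would not mistake harm for benefit. Section 4.2.6 also introduces the quantity correctly, as evidence of an effect against none. The sentence about values above 1 is still wrong.

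The missing threshold for the trigger in 4.4 and 4.5 would remain if every Bayes factor were deleted, and nothing ties that trigger to the Bayes factor. It is dealt with here only because the same revision can close it.

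The power-prior analysis does not answer the point: it leaves the main-analysis Bayes factor as it is, and its source, mean, SD and discount are not stated.

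**Conclusion.** The point holds for the Bayes factor and its interpretation. Followed as written, the SAP yields a figure that is undefined under a flat prior, or set largely by an unstated width under a proper one. On the same illustrative data it runs from 17.9 (strong evidence of an effect) at SD 1 to 0.034 (29 to 1 against) at SD 1000. Reading a value above 1 as effectiveness is wrong for any prior that allows both signs.

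The exact figures rest on the assumed counts, the assumed intercept prior and the omission of the site effect. SD 100 and SD 1000 are illustrations of wide priors, not values from the SAP. The 1/SD behaviour depends on none of these choices. The effect estimate, the credible interval and the probability of direction are not at risk.

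**What to change.** Before unblinding:

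- Keep the non-informative prior for estimation.
- For the Bayes factor, state a proper prior (family, mean, SD) for the treatment effect on each outcome's link scale, and report results over a stated range of SDs. For a log odds ratio, Normal(0, 1) with SDs of 0.5 and 2.5 as alternatives is one example. Otherwise drop the Bayes factor.
- Reword 4.2.6 so that a value above 1 is evidence of a difference in either direction, to be read with the sign of the estimate.
- State in 4.2.4 and 4.2.5 that any strengthening of priors is limited to nuisance parameters and leaves the treatment prior fixed.
- In 4.4 and 4.5, define evidence of a treatment effect as the 95% credible interval excluding zero on the log odds ratio scale, not by the Bayes factor. Name the scale, because an HPD interval changes under transformation.
- Do not replace that rule with a probability of direction of at least 0.975. The two are not identical for an HPD interval, and a one-sided probability towards benefit cannot detect harm.

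The cost is SAP wording and a few extra model fits.
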